## 6.10 Dose Modifications

### 6.10.1 Non-immune-related Adverse Events

- Grade 1 or 2 toxicity: No requirement for dose delay or dose reduction. If the toxicity persists at Grade 2 following completion of Cycle 1, a dose reduction to the next lower NKTR-214 dose level (for dose escalation) or 50% of the assigned dose (dose escalation or dose expansion) may be implemented at the discretion of the Investigator with the approval of the Medical Monitor.
- Grade 3 toxicity: NKTR-214 may be withheld if toxicity cannot be managed by adequate medical intervention. NKTR-214 dosing may resume at the same dose or the next lower NKTR-214 dose level (for dose escalation) or 50% of the assigned dose (dose escalation or dose expansion) when toxicity resolves to Grade 1 or returns to baseline, except for instances consistent with clinically significant capillary leak syndrome or where the potential recurrence of the event poses an undue risk for the subject.
- Grade 4 toxicity (excluding Grade 4 transient lymphopenia < 14 days in duration): Dosing should be permanently discontinued.

### 6.10.2 Immune-related Adverse Events

Permanently discontinue NKTR-214 for:

- Grade 2 or 3 immune-related AEs (irAEs) that do not improve to Grade 0 or 1, except endocrinopathies managed with replacement hormones
- Grade 3 irAEs that recur at  $\geq$  Grade 3
- Grade 3 immune-related pneumonitis, colitis, hepatitis, pancreatitis

- Grade 4 irAEs, except endocrinopathies managed with replacement hormones
- Any uveitis event

Subjects who need more than 6 weeks to recover from treatment-related toxicities should be removed from study treatment.

### **6.11 Administration of NKTR-214**

The subject's weight in kilograms will be determined before the start of each cycle. Each subject's NKTR-214 dose will be determined by the dose escalation scheme and the subject's weight in kilograms. NKTR-214 will be administered as an intravenous (IV) infusion over  $15 \pm 5$  minutes.

Pre-medications should not be administered prior to the initial administration of NKTR-214, but if a subject reports symptoms (such as nausea and/or vomiting), prophylactic use of anti-emetics may be used.

The administration of NKTR-214 will be captured in the source documents and recorded on the electronic case report form (eCRF). The lot number for the NKTR-214 vials will be captured on Drug Accountability Log.

Refer to the Pharmacy Binder for further information.

### **6.12 Infusion Delays and Missed Doses**

In exceptional circumstances, NKTR-214 administration may be delayed. NKTR-214 administrations that cannot be done within 7 days will be considered a missed dose, and the subject should come in for their next, regularly scheduled visit. The next scheduled visit should occur according to the subject's next regularly scheduled visit relative to Day 1. The Medical Monitor should be notified if a subject misses 3 consecutive doses. If a subject misses multiple consecutive doses of study drug, the subject may be considered discontinued with Medical Monitor approval.

### **6.13 Prior and Concomitant Medications**

All medications (prescription and over-the-counter [OTC]), vitamin and mineral supplements, and/or herbs taken by the subject from Screening through the EOT visit will be documented, and recorded on the concomitant medication eCRF and will include start and stop date, dose and route of administration, frequency and indication. Medications taken for a procedure (e.g., biopsy) should also be included.

#### **6.14 Permitted Medications**

Throughout the study, Investigators may prescribe any concomitant medications or treatments deemed necessary to provide adequate supportive care (including flu vaccines). All concomitant medications administered to study subjects will be captured in source documents and recorded on the eCRF.

#### **6.15 Prohibited Medications**

Any anti-cancer therapy (other than NKTR-214), investigational agent, or radiation therapy is prohibited during the study. Palliative radiation is permitted to 1 non-target lesion at a time, provided it is completed 14 days before dosing of NKTR-214. Subjects with pre-existing adrenal impairment requiring corticosteroid supplementation may be at increased risk for hypotensive episodes during treatment with NKTR-214. For these subjects, their existing corticosteroid dose may be increased by an additional supplementation of up to 5 mg/day of prednisone, or equivalent, for the first 4 days after administration of NKTR-214 based on an assessment of the degree of adrenal impairment and the extent of existing corticosteroid supplementation.

Consideration should be given to discontinuing antihypertensive medications including diuretics, as well as other drugs with hypotensive properties (e.g., alpha blockers for BPH), prior to each dose of NKTR-214, particularly when therapy involves multiple antihypertensive drugs and classes other than thiazide diuretics. Antihypertensive medications should be discontinued no less than 12 hours and no more than 48 hours prior to each dose of NKTR-214.

Antihypertensive medications may be reinstated in between doses of NKTR-214 if the diastolic pressure exceeds 90 mmHg and/or the systolic pressure exceeds 160 mmHg.

#### **6.16 Adverse Events**

All AEs, either reported by the subject or observed by study staff, will be recorded in the source documents and in the eCRF. This trial will use the Medical Dictionary for Regulatory Activities (MedDRA 18.1 or later) for coding all AEs. AEs within each system will be summarized by preferred term, system organ class, NCI-CTCAE version 4.03 grade of severity, and relationship to the study drug.

#### **6.17 Assigning Subject Numbers**

Each subject will be assigned a unique subject number after signing the ICF. This subject number will be used on all subjects' study information. Subject numbers will not be reassigned.

## **7.0 INVESTIGATIONAL PRODUCT(S)/STUDY DRUGS**

### **7.1 Description and Formulation**

The investigational drug product, NKTR-214, is formulated as a sterile lyophilized powder for reconstitution in single-use glass vials. Lyophilized NKTR-214 drug product will be diluted with commercially available Dextrose 5% in water for injection (D5W). Each 5 mL, clear glass, single-use vial contains 1.1 mg of recombinant human interleukin 2 (rhIL-2) equivalence (including 0.1 mg of overage). NKTR-214 is formulated in 10 mM citrate buffer, 7% (w/v) trehalose, pH 4.0.

### **7.2 Study Drug Packaging and Labeling**

The study drug will be packaged and labeled according to current good manufacturing practices (cGMP). The lyophilized drug product is packaged in a Schott 5 mL, 13 mm opening, USP Type I glass serum lyophilization vial with 13 mm Westar® coated gray rubber stoppers and aluminum crimps with flip cap. Secondary packaging will be cardboard box with foam inserts holding up to 10 vials.

Each vial will be labeled with the study drug number/name, strength, name of the Sponsor, storage condition, lot number and the required cautionary statement.

### **7.3 Study Drug Reconstitution and Handling**

The instructions for reconstitution and administration of NKTR-214 drug product are described in the Pharmacy Manual.

### **7.4 Study Drug Storage**

NKTR-214 drug product should be stored in a secure, locked area with temperature at -20°C (± 5°C), as specified on the drug label.

### **7.5 NKTR-214 Drug Shipment**

Supply of NKTR-214 drug product will be shipped frozen (-20°C) to the site pharmacy upon completion of the site activation process.

Please refer to the Pharmacy Manual for additional details for ordering drug supply.

## 7.6 Study Drug Accountability and Reconciliation

All study drug will be supplied to the Investigator by Nektar Therapeutics or its designee. Study drug supplies must be kept in an appropriate, secure locked area and stored in accordance with the conditions specified on the labels.

The Investigator, pharmacist, or designee must maintain an accurate record of dispensing the study drug in a Drug Accountability Log, a copy of which must be given to Nektar Therapeutics at the end of the study.

The Drug Accountability Log may record specifics to study drug dispensation such as:

- Records of product delivery, inventory, temperature monitoring, destruction, and return as per Sponsor's instructions
- Dosages prepared, time prepared, doses dispensed
- Doses and/or vials destroyed

The Drug Accountability Log will be reviewed by the field monitor during site visits and at the completion of the study.

## **8.0 ASSESSMENT OF SAFETY OR AES AND SERIOUS AES**

### **8.1 AE Definition and Assessment**

An AE is defined as any untoward medical occurrence in a clinical investigation subject administered a pharmaceutical product, at any dose, not necessarily related to the treatment.

An AE can therefore be any unfavorable and unintended sign, symptom, or disease temporally associated with the use of a medicinal product, whether or not considered related to the medicinal product. An AE can also arise from any use of the drug and from any route of administration, formulation, dose, or overdose. This definition includes intercurrent illnesses or injuries, and exacerbation of preexisting conditions. Clinical laboratory abnormalities will only be reported as AEs if they are deemed clinically significant by the Investigator and/or are associated with signs and symptoms, require treatment, or require follow-up.

An AE does not include:

- A medical or surgical procedure (e.g., surgery, endoscopy, tooth extraction, or transfusion); an AE is the underlying condition that leads to the procedure
- Pre-existing diseases or conditions present or detected before start of study medication administration which do not worsen or increase in severity or frequency after the administration of study medication
- Situations where an untoward medical occurrence has not occurred (e.g., hospitalization for elective surgery for a condition that has not worsened on study, social and/or convenience admissions to grant families a respite in caring for a subject)
- Overdose of either study medication or concomitant medication without any signs or symptoms

### **8.2 Monitoring AEs**

All AEs will be assessed by the Investigator and recorded on the appropriate eCRF including but not limited to, the following: the event term, the date of onset and resolution, seriousness, severity, relationship to study drug, outcome, treatment of the event, and action taken with the study drug. AEs will be reported starting immediately after the subject has been administered the first dose of study medication through 30 days after the last dose of NKTR-214.

An event occurring after the subject has provided informed consent, but before the first dose of study treatment, will be collected as medical history unless the event is either new and attributed to protocol-mandated procedures by the Investigator OR there is a significant change in the rate

of occurrence or an increase in the severity of the pre-existing condition which is judged to be clinically important and attributed to the protocol-mandated procedures by the Investigator. Under the latter two circumstances, the event will be considered an AE and will be captured as such on the eCRF.

Example 1:

*Thrombophlebitis associated with a blood draw for assessments required prior to dosing per protocol is an event that is related to protocol-mandated procedures. In this scenario, the event of “thrombophlebitis” will be captured as an AE on the eCRF page, and it will be documented as being “unrelated” to study drug as applicable.*

Example 2:

*An ankle sprain following an unexpected fall from a flight of stairs while at home, after the subject has provided informed consent, but before the first dose of study drug, is clearly unrelated to any protocol-mandated procedures and would therefore be captured as medical history in the medical history section of the eCRF.*

### 8.3 Grading of AEs

The severity of an event and the seriousness are not to be considered synonymous. The severity is grading the intensity of an event. The seriousness of event is based on the subject/event outcome or action criteria. All AEs will be assessed for severity using the NCI-CTCAE version 4.03. If a particular AE is not listed in the NCI-CTCAE, the following criteria will be used:

- Grade 1 = Mild (event results in mild or transient discomfort, not requiring or needing only minimal intervention or treatment; does not limit or interfere with daily activities (e.g., insomnia, mild headache)
- Grade 2 = Moderate (event is sufficiently discomforting so as to limit or interfere with daily activities; may require interventional treatment (e.g., fever requiring antipyretic medication)
- Grade 3 = Severe (event results in significant symptoms that prevents normal daily activities; may require hospitalization or invasive intervention).
- Grade 4 = Life threatening or disabling
- Grade 5 = Death

AEs will be reported with an individual start and stop date for each level of severity.

#### **8.4 Causality Relationship of AEs**

The relationship of each AE to the study treatment (NKTR-214) as applicable will be evaluated by the Investigator using the following definitions:

- Not related: The AE is clearly not related to the investigational agent(s). The AE can be explained to be likely related to other factors such as concomitant medications or the subject's clinical state.
- Possibly related: The AE may be related to the investigational agent(s). A plausible temporal sequence exists between the time of administration of the investigational product and the development of the AE and it follows a known response pattern to the investigational product. The reaction may have been produced by the subject's clinical state or other concomitant therapies or interventions.
- Related: The AE is clearly related to the investigational agent(s). A plausible temporal sequence exists between the time of administration of the investigational product and the development of the AE and it follows a known response pattern to the investigational product. The occurrence of this AE can be confirmed with a positive re-challenge test or supporting laboratory data.

The causality criteria of related and possibly related will be considered "related" to the study medication for regulatory reporting requirements.

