### 2.3 Starting Dose Rationale

The planned Phase 1 NKTR-214 starting dose of 0.003 mg/kg is 1/10th of the cynomolgus monkey MTD (0.1 mg/kg) that has been corrected for body surface area. A dose of 0.003 mg/kg is expected to be active in humans since it is the lowest dose tested in the monkey toxicology study at which increases in both sCD25 (10-fold) and lymphocyte counts (2-fold) were observed. A dosing schedule of q21d was chosen for the first in human study based on the histopathologic changes (inflammatory cell infiltrates) in monkeys 14 days after administration of the last q14d NKTR-214 dose that almost completely resolved with an additional 4 weeks of recovery (6 weeks following the last dose). [Table 3](#) shows the safety margins for the proposed clinical starting dose of NKTR-214.

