A DLT is defined as a Grade 3 or higher study drug-related or possibly related AE occurring within the first cycle of dosing (excluding Grade 3/4 transient lymphopenia < 14 days in duration, tumor flare defined as local pain, irritation, or rash localized at sites of known or suspected tumor, a transient, reversible  $\leq$  grade 3 infusion AE [ $<$  24 hours], non-clinically significant laboratory abnormalities, or fatigue lasting less than 72 hours) using National Cancer Institute (NCI) Common Terminology Criteria for AEs (CTCAE) version 4.03.

All drug related AEs after Cycle 1 will continue to be collected and evaluated by the Investigators and the Sponsor on an ongoing basis and may be taken into consideration in determining the MTD.

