#### 10.2.1 Expansion Cohorts Safety Monitoring

Bayesian sequential monitoring will be employed to perform ongoing safety monitoring targeting a toxicity rate of not more than 30% (where toxicity follows the same definition as a DLT defined in Section [4.1.2.1](#)) for the first 80 subjects enrolled in the dose expansion phase. Subjects will be monitored across tumor-specific cohorts after a minimum of 6 subjects treated at the selected dose for the dose expansion phase. The criteria for suspending enrollment due to safety are included in [Table 7](#) based on Bayesian sequential monitoring designs by [Thall et al. \(1995\)](#). The determination of the criteria is when:

$$\Pr [\text{prob}(\text{toxicity}) > 0.30 \mid \text{data}] > 0.95.$$

If there is a greater than 95% chance that the toxicity rate is greater than 30%, then accrual will be suspended and the safety review committee will meet to review safety data including aggregated safety summaries. We assume a beta (0.6, 1.4) prior distribution for the toxicity rate,

which has a mean of 0.3 corresponding to the 30% target toxicity rate. A constant 30% rate was chosen for the standard treatment rate.

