10.2 Adverse Events

A treatment emergent adverse event (TEAE) is:

- an AE that was not present prior to treatment and occurred after the first dose of NKTR-214 including partial dose or
- a pre-existing condition that was present before first dose of NKTR-214 and worsened after the first dose of NKTR-214 or
- an AE that was present at treatment initiation, but resolved and then reappeared while the subject was on treatment (regardless of intensity of the AE when the treatment was initiated)

In addition, an AE will be considered to be a TEAE if its status cannot be fully determined due to incomplete data. All AEs will be coded by MedDRA using SOC and PT. Only TEAEs will be summarized in the table. All AEs including non-TEAEs will be listed by subject.

An AE is considered to be related to NKTR-214 if the relationship to study treatment is assessed by investigators as possibly related or related. An AE with missing or unknown relationship will be considered to be a related AE.

For each NKTR-214 related TEAE, the duration of TEAEs will be summarized by SOC and PT. The duration of the NKTR-214 related TEAEs will be calculated as:

$$\text{Duration of AE} = \text{AE stop date} - \text{AE start date} + 1.$$

For subjects who have the same NKTR-214 related TEAE multiple times, the duration will be the average of each individual duration. An incomplete start and end date for a NKTR-214 related TEAE will be imputed as specified in Section 6. The duration of AEs will be summarized by SOC and PT.

A TEAE is considered to be a TEAE leading to death if the severity grade is 5 or the outcome is fatal. A TEAE is considered to be a TEAE leading to NKTR-214 discontinuation if the action taken to NKTR-214 is drug withdrawn. A TEAE is considered to be a TEAE leading to NKTR-214 delay, reduction, or interruption if the action taken to NKTR-214 is dose delayed, dose reduced, or dose interruption.

In each summary table, the total number of events and the number and percentage of subjects who have at least one event will be reported. For TEAE summaries by SOC and/or PT, a subject is counted only once within each summary level. For TEAE summary by CTCAE grade, a subject is counted only once using the highest grade.

The following summaries will be provided for AEs:

- TEAEs by SOC and PT,
- TEAEs by PT,
- TEAEs by severity grade, SOC, and PT,
- TEAEs by severity grade, SOC, and PT in cycle 1,
- NKTR-214 related TEAEs SOC and PT,
- NKTR-214 related TEAEs by PT,

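### The causality scale in Protocol 8.4 has no category that fits a plausibly timed toxicity of a new kind, so such an event can be recorded as not related and leave the DLT count

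*Protocol*

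**What the plan says.** Protocol 8.4 tells the investigator to judge each event against three definitions.

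- *Not related*: the event is clearly not related and can be put down to other factors, such as concomitant medication or clinical state.
- *Possibly related*: the event may be related, there is a plausible time sequence, and "it follows a known response pattern to the investigational product. The reaction may have been produced by the" subject's clinical state or other treatment.
- *Related*: the event is clearly related, the time sequence is plausible, and "it follows a known response pattern to the investigational product. The occurrence of this AE can be confirmed with" a positive re-challenge or laboratory support.

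There is no *unlikely* or *unknown* category.

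These grades feed the decision rules. Protocol 4.1.2.1 says: "A DLT is defined as a Grade 3 or higher study drug-related or possibly related AE occurring within the first cycle of dosing", followed by a list of exclusions. The Synopsis, Protocol 6.9 and SAP 10.1 also make relatedness part of the definition. Protocol 10.2.1 uses it for expansion monitoring, "where toxicity follows the same definition as a DLT defined in Section" 4.1.2.1. SAP 10.2 builds its related-event tables the same way: "An AE is considered to be related to NKTR-214 if the relationship to study treatment is assessed by investigators as possibly related or related". It adds that missing or unknown causality counts as related.

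Protocol 2.3 gives the setting: "A dosing schedule of q21d was chosen for the first in human study".

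**The concern.** The middle category of a causality scale should take the uncertain cases. Here it carries a condition that a new kind of toxicity fails by its nature, because the first occurrence has no known pattern to follow. Dose finding in a first-in-human study exists partly to detect such toxicities.

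If the event is recorded as not related, it is not a DLT under Protocol 4.1.2.1, does not count towards Table 7 and is absent from the related-AE tables. Events lost in this way can only make a dose look safer: escalation becomes easier and suspension harder. The outcome may also vary between sites (about 3 in escalation and up to 15 more in expansion), depending on how literally each one reads 8.4.

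**Working it through.** **Step 1: the definitions, applied to one case.** Take a Grade 3 event in Cycle 1 with plausible timing, no obvious other cause, and no precedent with this product.

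- *Related*: fails, because there is no known pattern.
- *Possibly related*: the opening statement that the event may be related fits and the timing fits. The pattern condition is joined by *and*, and it fails.
- *Not related*: fails, because the event is not clearly unrelated.

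The event has no valid category, so the entry depends on which definition the investigator chooses to stretch.

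**Step 2: does another provision return the event to the count?**

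- SAP 10.2 (missing or unknown counts as related) works only if the field is blank or unknown. It is an analysis rule and has no effect once *Not related* is entered.
- Protocol 6.9 opens its DLT definition with an exception for clinical data, but does not mention causality.
- The rule in 6.9 that ignores attribution concerns 24-hour reporting of Grade 3 or higher immune-related events, not DLT counting.
- AEs after Cycle 1 that may inform the MTD (Protocol 4.1.2.1, 6.9; SAP 3) are drug-related ones, so they pass through the same scale.
- The safety review committee (Protocol 10.2.1) sees the data, but no rule lets it reclassify an event for the count.

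**Step 3: reproduce the plan's own figures.** Inputs from Protocol 10.2.1: Beta(0.6, 1.4) prior, and suspension when Pr(rate > 0.30 | data) > 0.95. The boundary at n is the smallest x for which the Beta(0.6 + x, 1.4 + n − x) probability above 0.30 exceeds 0.95. All 74 boundaries from n = 6 to 79 match Table 7. An exact binomial recursion, checked after every subject from n = 6 up to 80, gives suspension probabilities of 0.0005, 0.0181, 0.2019, 0.7593, 0.9905 and 1.0000 for true rates 0.1 to 0.6. Table 8 prints 0.001, 0.018, 0.202, 0.759, 0.991 and 1.000. The sample-size percentiles agree within 2 subjects.

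**Step 4: sensitivity to lost events.** Let p be the true DLT rate and f the share of subjects with a DLT whose event is recorded as not related. The rules then see p(1 − f). The documents give no f, so the values below are assumptions. From Table 5, a dose is passed with 0 of 3 DLTs, or with 1 of 3 followed by 0 of 3:

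P(escalate) = (1 − q)³ + 3q(1 − q)² × (1 − q)³, with q = p(1 − f).

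At q = 0.40: 0.216 + 0.432 × 0.216 = 0.309. At q = 0.30: 0.343 + 0.441 × 0.343 = 0.494.

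Results for p = 0.40:

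| f (assumed) | q | 3+3 escalates | Suspended within 50 | Suspended within 80 |
|---|---|---|---|---|
| 0 | 0.40 | 0.309 | 0.622 | 0.759 |
| 0.10 | 0.36 | 0.378 | 0.422 | 0.528 |
| 0.25 | 0.30 | 0.494 | 0.173 | 0.202 |
| 0.50 | 0.20 | 0.709 | 0.018 | 0.018 |

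The 50-subject column matches the planned size of Part 2. In the 80-subject column, the rows for q = 0.40, 0.30 and 0.20 can be read from Table 8. With 10% lost, the chance of suspension within 50 falls by about a third: (0.622 − 0.422) / 0.622 = 0.32.

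**The case against.** A reader might infer that 8.4 sends every new toxicity to *Not related* as the only box left. The documents do not support that. *Not related* is strict, and a well-timed severe event with no other explanation fails it as well. *Possibly related* opens permissively, and many investigators would probably choose it. A blank or unknown entry would count as related under SAP 10.2. Undercounting therefore needs an investigator to enter a category whose own condition is not met. This part of the objection stands: the defect is a gap, not an instruction to discard events.

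Nor is it right to say that nothing is known. The pattern in 8.4 is to the product and is not limited to human experience. Protocol 2.1 describes the shared IL-2 sequence with aldesleukin and lists that drug's toxicities. Protocol 2.2.3 gives rat and monkey findings, and SAP Appendix 16.2 lists events of special interest. About 50 escalation subjects should have been treated by the time Part 2 opens. This narrows the affected events to those outside the existing picture. It does not remove them, and 8.4 does not say whether class or animal findings count as a known pattern.

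The loss shares are assumed, and they are held constant although a recurring toxicity would become known. SAP 3 also treats 3+3 as a guide. The Sponsor and an investigator may lower a planned dose level on observed toxicities without a relatedness condition (Protocol 4.1.2.1), and SAP 10.2 tabulates events of any cause by grade. A misattributed event would therefore remain visible to safety reviewers, but none of this puts it back in the DLT or Table 7 count.

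**Conclusion.** The concern holds as a gap in a written rule. By its terms, 8.4 leaves a plausibly timed, new kind of toxicity without a valid causality category, and a literal reader may record it as not related. The DLT count, the Table 7 count and the related-AE tables all depend on that entry, and no other provision restores the event to the counts once it is made.

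The size is unknown. The figures above show how sensitive the two rules are if 10%, 25% or 50% of DLTs were lost at a true rate of 0.40. They do not predict that such shares will be lost, and a reader should not infer that the trial will miss a quarter or half of its DLTs. The illustration is weakest for Part 2, where more of the drug's pattern will be known.

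The change should be made: the wording is plainly defective, any error runs towards making a dose look safer, and the repair is small.

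**What to change.** In Protocol 8.4, under *Possibly related*, delete the clause requiring a known response pattern and keep the plausible time sequence. Keep the following sentence, which allows that clinical state or other therapies may have contributed; without it the category could become narrower than it is now. Then add one sentence: *Any event that does not meet the definition of clearly not related is to be recorded as at least possibly related.* Put the same instruction in the eCRF guidance.

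The added sentence must govern how the investigator records the event. A rule applied only when DLTs are counted would not recover an event already entered as *Not related*. The known-pattern clause may stay under *Related*, since *Possibly related* is enough for every count discussed here. The DLT definition and its listed exclusions stay unchanged.

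The cost is one deletion, one sentence and matching guidance to sites. The downside is that a few more events will be counted as related.
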